# 7 TOXICITIES AND DOSEAGE MODIFICATION

This study will utilize the CTCAE (NCI Common Terminology Criteria for Adverse Events) Version 4.0 for adverse event and serious adverse event reporting. A copy of the CTCAE Version 4.0 can be downloaded: (http://safetyprofiler-ctep.nci.nih.gov/CTC/CTC.aspx).

# 7.1 **Dose Modifications**

#### 7.1.1 Nivolumab

Recommendations for nivolumab dose modifications are listed in the table 1 below.

#### Table 1: Recommended Dose Modification for Nivolumab
Protocol name: Phase II Neoadjuvant trial of Nivolumab in Combination with HF10 Oncolytic Viral Therapy in Resectable Stage IIIB, IIIc, IVM1a Melanoma (Neo-NivoHF10) Version Date: 22JUL2019 Principal Investigator: [name]

Adverse Reaction	Severity*	Dose Modification
Colitis	Grade 3 diarrhea or colitis	Withhold dose a
	Grade 4 diarrhea or colitis	Permanently discontinue
Pneumonitis	Grade 2 pneumonitis	Withhold dose a
	Grade 3 or 4 pneumonitis	Permanently discontinue
Hepatitis	Grade 2 AST or ALT or total bilirubin increased	Withhold dose a
	Grade 3 or 4 AST or ALT or total bilirubin	Permanently discontinue
Hypophysitis	Grade 2 or 3 hypophysitis	Withhold dose a
	Grade 4 hypophysitis	Permanently discontinue
Adrenal Insufficiency	Grade 2 adrenal insufficiency	Withhold dose a
	Grade 3 or 4 adrenal insufficiency	Permanently discontinue
Type 1 Diabetes Mellitus	Grade 3 hyperglycemia	Withhold dose a
	Grade 4 hyperglycemia	Permanently discontinue
Nephritis and Renal Dysfunction	Grade 2 or 3 Serum creatinine	Withhold dose a
	Grade 4 Serum creatinine	Permanently discontinue
Skin	Grade 3 rash or suspected Stevens-Johnson syndrome (SJS) or toxic epidermal necrolysis (TEN)	Withhold dose a
	Grade 4 rash or confirmed SJSor TEN	Permanently discontinue
Encephalitis	New-onset moderate or severe	Withhold dose a

	neurologic signs or symptoms	
	Immune-mediated encephalitis	Permanently discontinue
Other	Other Grade 3 adverse reaction First occurrence Recurrence of same Grade 3 adverse reactions	Withhold dose a Permanently discontinue
	Life-threatening or Grade 4 adverse reaction	Permanently discontinue
	Requirement for 10 mg per day or greater prednisone or equivalent for more than 12 weeks	Permanently discontinue
	Persistent Grade 2 or 3 adverse reactions lasting 12 weeks or longer	Permanently discontinue

\* Toxicity was graded per National Cancer Institute Common Terminology Criteria for

Adverse Events. Version 4.0 (NCI CTCAE v4).

a Resume treatment when adverse reaction returns to Grade 0 or 1.

If nivolumab is withheld for more than 12 weeks, the treatment will be permanently discontinued.

In the event of a nivolumab dose delay, the concurrent HF10 dose will be similarly delayed; the HF10 dose will then be administered on the same day that nivolumab is administered.

# 7.1.2 HF10

In the event that the patient is unable to tolerate HF10 (grade 2 intolerable or higher chills, injection site disorders, fatigue, malaise, pyrexia, nausea, dehydration, pruritus, and/or hypotension which do not respond to optimal management) at the discretion of the treating provider, the dose will be reduced to  $1 \times 10^{6}$  TCID50/mL. The HF10 product will be diluted with physiological saline just before use to meet the target dose level. Specific instructions will be provided in the Pharmacy Manual.

If the patient is unable to tolerate the reduced dose the patient will be withdrawn from treatment.

## 7.2 **Subject Compliance**

Both Nivolumab and HF10 will be dispensed from the Huntsman Cancer Institute Investigational Pharmacy and administered by a study investigator, thus ensuring compliance with therapy parameters.

# 7.3 Patient Precautions for Minimizing Virus Exposure to Others

The HSV-1 virus, from which the study drug HF10 is derived, is very widespread in the environment, and many people in the United States have been exposed to HSV-1. HF10 is a weakened strain of HSV-1 and is believed to pose minimal health risk. No association of HF10 with any human illness has been established. However, given the investigational nature of HF10 therapy, it is appropriate that HF10-treated patients follow some precautions for minimizing HF10 exposure to persons with whom they have close contact. Appendix I provides guidance for the patient for minimizing exposure of HF10 to others.

## 7.4 Healthcare Provider Precautions

HF10 is a replication-competent virus. Although it is believed that the risk of inadvertent infection to study staff is extremely low, infectious disease precautions should be implemented to minimize viral exposure to healthcare providers. In the event of an accidental spill of HF10 containing solution, standard biohazard waste procedures should be employed, including use of gloves, gown, and mask, by healthcare workers coming in contact with or disposing of the study drug product. Contaminated surfaces should be first washed with a 10% sodium hypochlorite solution, followed by rinsing with water, and finally with 70% ethanol. All tubing and other disposables that may have been in contact with HF10 must be discarded as biohazardous waste.

In the event of an accidental needle stick, the healthcare provider should report the incident and follow the institutional inadvertent needle stick exposure policy implemented at the study site. In the event of inadvertent contact with HF10 (e.g., accidental spill, body fluid contact, or needle stick), exposed individuals may be treated, if warranted, with acyclovir, famciclovir, or valacyclovir. HF10 has been demonstrated to be sensitive to these anti-herpes agents. Treatment recommendations would follow those for acute wild type HSV infection.

An additional precaution recommended in this clinical trial is that pregnant healthcare providers be excluded from participating in the administration of HF10 or the care of HF10-treated patients. Although preclinical data indicate that HF10 does not undergo germline genomic integration, potential risks of HF10 to the developing human fetus have not been determined.

## 7.5 Supportive Care

All supportive measures consistent with optimal patient care will be given throughout the study.

Management of immune mediated events (irAEs) will follow the package inserts for the Nivolumab products.

Protocol name: Phase II Neoadjuvant trial of Nivolumab in Combination with HF10 Oncolytic Viral Therapy in Resectable Stage IIIB, IIIc, IVM1a Melanoma (Neo-NivoHF10) Version Date: 22JUL2019 Principal Investigator: [name]

#### HUNTSMAN CANCER INSTITUTE UNIVERSITY OF LITAH 8 STUDY CALENDAR

Examination	Pre- study 	D0	D7±4 and D21±4	D14±4 and D28±4	D42±4	D56±4 and D70±4	D84±4	Surgery 	Every 4 wks ±2 wks for one year 	EOT  or Progression	Follow- up 
Informed consent	Х										
Medical history	Х										
Concomitant Medications	Х	Х	Х	Х	Х	Х	Х		Х	Х	Х
Eligibility criteria	Х										
Vital signs 	Х	Х	Х	Х	Х	Х	Х		Х	Х	
Height	Х										
Weight	Х	Х		Х	Х	Х	Х		Х	Х	
Physical examination	Х	X 	Х	Х	Х	Х	Х		Х	Х	
Lesion Photography 	Х			Х	Х		Х				
CBC/differential platelet count	Х	X 	Х	Х	Х	Х	Х		Х	Х	
Chemistry 	Х	X 	Х	Х	Х	Х	Х		Х	Х	
Pregnancy Test (serum or urine)	X 	X 					Х		X 		
Thyroid function tests 	X		Х		Х		Х				
PT/INR in patients receiving warfarin anticoagulation therapy	Х	Х	X	Х	Х	Х	X				
LDH	X						X			Х	
Genomic testing 	Х										
Adverse Event Assessment 		Х	Х	Х	Х	Х	Х	Х	Х	Х	Х
Radiologic Evaluation 	Х						Х		X 	Х	
irRC 	Х						Х				
RECIST 1.1 	Х						Х				
Biopsy for correlative studies 		Х			Х			Х		Х	
Blood for correlative studies 		Х	Х	Х	Х	Х	Х		Х		
Nivolumab		Х		Х	Х	Х	Х		Х		
HF10 injections		Х	Х	Х	Х	Х	Х				
Surgery								X 			

Protocol name: Phase II Neoadjuvant trial of Nivolumab in Combination with HF10 Oncolytic Viral Therapy in Resectable Stage IIIB, IIIc, IVM1a Melanoma (Neo-NivoHF10) Version Date: 22JUL2019 Principal Investigator: [name]

Study visits during neoadjuvant nivolumab are scheduled in days. Windows are  $\pm$  business days.

- 1 ALL Pre-study/Screening procedures should be completed within 28 days of study enrollment
- 2. Does not need to be done if occurred 7 days before D0.
- 3. Includes temperature, blood pressure, and pulse rate.
- 4. Chemistry includes: Albumin, Alkaline Phosphatase, Aspartate Aminotransferase (AST), Alanine Aminotransferase (ALT), Total Bilirubin, Calcium, Carbon Dioxide, Creatinine, Chloride, Glucose, Potassium, Protein, Sodium, Urea Nitrogen. Fasting Glucose will be tested as clinically indicated.
- 5. A scan of the chest abdomen and pelvis with extension to the extremities if applicable. The same method (CT scans or possibly PET/CT scan) should be used for all assessments.

6. Biopsies are mandatory at day 0 and surgery. Biopsies are optional at day 42 and progression. See section 13.1 for details about the collection.

7. Adverse events will be followed until resolution while the patient remains on treatment. Events will be followed for 90 post treatment for SAEs and events thought to be related to the study medication will be followed until resolution or stabilization of the adverse event, or until the patient starts a new treatment regimen.

8. Surgery should occur no later than 28 days after D84.

9. Adjuvant nivolumab should be initiated within 90 days after definitive surgery.

10. EOT visit should occur 28 days (+-14 days) after the completion of therapy.

11. Follow-up should occur every three months (+-or 14 days) for 1 years post EOT visit.

12. Surgery will reset the scan schedule and should occur approximately every 12 weeks after surgery as standard of care.

13. Pathology at surgery will be used to determine pathological response.

14. Collection of blood samples for correlatives is optional and will be collected prior to HF10 injection during the neo-adjuvant (days 0,7, 14, 21, 28, 42, 56, 70, 84) and prior to nivolumab infusion during the adjuvant nivolumab administration.

15. Men and women of childbearing potential must agree to use adequate contraception from the time of consent through 7 months after nivolumab study treatment (neoadjuvant and adjuvant). A pregnancy test will be conducted w/in 72 hours prior to beginning adjuvant nivolumab.

16. Next generation sequeencing is required at screening as per standard of care. Testing will include, but is not limited to BRAF mutational analysis.

17. Thyroid Tests will include TSH and free T4. In the event of hypo/hyper thyroidism, appropriate support will be provided in accordance with institutional guidelines.

18. Lesion photography should be completed at each time point AND when a new lesion is identified.

19. irRC and RECIST should be done prior to surgery. Only RECIST will be used as clinical response criteria and used to make treatment decisions

Protocol name: Phase II Neoadjuvant trial of Nivolumab in Combination with HF10 Oncolytic Viral Therapy in Resectable Stage IIIB, IIIc, IVM1a Melanoma (Neo-NivoHF10) Version Date: 22JUL2019 Principal Investigator: [name]

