# 6.1.3 Adjuvant treatment

#### Nivolumab

Adjuvant nivolumab should be initiated within 90 days after definitive surgery. Nivolumab will be administered at a flat dose of 480 mg IV every 28 days (every 4 weeks) for one year. We have chosen the 480mg IV dose every 4 weeks in accordance with the application made by Bristol-Myers Squibb to the FDA on July 24, 2017. This dose will be similar to the current FDA approved dose of 240 mg IV every 2 weeks with fewer infusions for the patient.

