## **Safety Laboratory Determinations**

Laboratory evaluations will be performed as noted in the study calendar.

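### No thyroid test is scheduled in the adjuvant year or at end of treatment, although nivolumab continues at the same dose rate

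*Combined protocol and SAP*

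**What the plan says.** - **Tests and schedule.** The Section 8 calendar has a row headed "Thyroid function tests", marked at pre-study, D7/D21, D42 and D84. It is blank at surgery, the four-weekly adjuvant visits, EOT/progression and follow-up. Footnote 17 gives the content but no timing: "Thyroid Tests will include TSH and free T4. In the event of hypo/hyper thyroidism, appropriate support will be provided" (the sentence goes on to refer to institutional guidelines).
- **Other laboratory rows.** CBC and chemistry are marked at the adjuvant visits and at EOT. The chemistry panel is listed in footnote 4, beginning "Chemistry includes: Albumin, Alkaline Phosphatase, Aspartate Aminotransferase (AST), Alanine Aminotransferase (ALT), Total Bilirubin, Calcium". The full list contains neither TSH nor T4.
- **Which document governs.** Section 9.2 says: "Laboratory evaluations will be performed as noted in the study calendar".
- **Treatment.** Section 6.1.1 gives seven infusions of 240 mg at 14-day intervals before surgery. Section 6.1.3 then says: "Nivolumab will be administered at a flat dose of 480 mg IV every 28 days (every 4 weeks) for one year". It adds: "This dose will be similar to the current FDA approved dose of 240 mg IV every 2 weeks with fewer infusions for the patient".
- **Safety objective and analysis.** Objective 1.2.5 covers the adjuvant phase as well as the neoadjuvant phase. Section 10 makes the safety analysis descriptive.

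**The concern.** The plan tests thyroid function on a schedule during the 12 neoadjuvant weeks and then stops, while the same drug runs on for a year at the same rate. The protocol gives no reason for stopping. Footnote 17 promises support if thyroid dysfunction occurs, but that depends on finding it.

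What is at stake is the safety record. Under Section 14.4.1 a laboratory abnormality is an adverse event if it causes signs or symptoms, is judged clinically significant, or needs therapy. An abnormality can therefore count without symptoms, and symptom-led detection may miss such a case or find it late. AE collection stays open until 30 days after the last adjuvant dose, so the reporting window outlasts the scheduled means of detection. The safety tables could then show thyroid events found by scheduled testing before surgery and mostly by symptoms or discretion afterwards.

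Minor changes that are neither symptomatic, clinically significant nor treated are not adverse events in either phase, so they are not part of this point.

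**Working it through.** **1. Is the gap real, or a table-reading error?** The calendar has 12 columns and the thyroid row has 12 cells, so nothing has shifted.

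| Row | Neoadjuvant marks | Surgery | Adjuvant visits | EOT |
|---|---|---|---|---|
| Thyroid | D7/D21, D42, D84 | – | – | – |
| CBC, chemistry | every visit, D0 to D84 | – | X | X |
| Nivolumab | D0, D14/D28, D42, D56/D70, D84 | – | X | – |

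The thyroid row also has a pre-study mark. Scheduled on-treatment thyroid tests are therefore 4 before surgery (D7, D21, D42, D84) and 0 in the adjuvant year.

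**2. Does nivolumab continue at the same rate?** This checks the plan's own statement that the two regimens are similar.
- Neoadjuvant: 240 mg / 2 weeks = 120 mg/week.
- Adjuvant: 480 mg / 4 weeks = 120 mg/week.

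The two rates are equal.

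**3. How much treatment falls after scheduled testing ends?** The protocol gives the adjuvant duration but no dose count, so 12 and 13 doses are both shown as assumptions. Neoadjuvant exposure is 7 × 240 = 1,680 mg.

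| Adjuvant doses (assumed) | Adjuvant mg | Share by mg | Share of infusions |
|---|---|---|---|
| 12 | 12 × 480 = 5,760 | 5,760 / 7,440 = 77.4% | 12 / 19 = 63.2% |
| 13 | 13 × 480 = 6,240 | 6,240 / 7,920 = 78.8% | 13 / 20 = 65.0% |

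Because the dose rate is the same, the share by mg reflects the length of the adjuvant phase, not a heavier dose.

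**4. How long is the gap before restart?** Footnote 8: "Surgery should occur no later than 28 days after D84". Footnote 9: "Adjuvant nivolumab should be initiated within 90 days after definitive surgery". The surgery column has no laboratory tests. The gap from D84 to restart is therefore up to 28 + 90 = 118 days.

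**5. How long is the gap from D84 to EOT?** EOT is taken at its nominal 28 days after the last dose.
- Shortest: 12 doses and no delay to surgery or restart: 0 + 11 × 28 + 28 = 336 days. This is a theoretical floor, since surgery and restart cannot both fall on D84.
- Both delays at their limits, 13 doses: 118 + 12 × 28 + 28 = 482 days. Visit windows and dose holds are left out and would lengthen this.

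**6. Does any other text fill the gap?**
- Section 9.2 permits extra evaluations when clinically indicated or at the investigator's discretion. It does not require them.
- Section 7.5 refers the management of immune-mediated events to the nivolumab package inserts. It sets no test schedule.
- Footnote 15 adds a pregnancy test within 72 hours before adjuvant nivolumab. No footnote does the same for thyroid tests.

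**The case against.** The strongest case on the other side accepts the calendar reading and disputes the consequence.

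- **Monitoring does not stop.** Vital signs, weight, physical examination and AE assessment continue at adjuvant visits and EOT, and AE assessment is also marked at surgery and follow-up. Investigators may order thyroid tests, and Section 7.5 promises supportive measures throughout. *This stands as mitigation. None of it schedules a TSH or free T4 measurement.*
- **The documents give little sign of the size of the risk.** The nivolumab safety summaries in Sections 2.4 and 3.2 name no thyroid event, and the Section 7.1.1 dose-modification table has no thyroid row. *This stands. The consequence is less certain than the calendar reading. However, footnote 17 itself anticipates thyroid dysfunction, and the plan thought it worth scheduled testing in the shorter phase.*
- **The effect is narrow.** It concerns asymptomatic but significant or treated changes that nobody tests for, in about 20 patients, within a descriptive analysis with no planned comparison between phases. *This stands, and it limits the weight of the point.*
- **An EOT test may fall outside AE collection.** EOT is 28 ± 14 days after therapy, so 14 to 42 days, while AE collection ends at 30 days. *This stands in part. The nominal EOT day is inside the window and AE assessment is marked at EOT, but a late EOT visit would not be. The marks before restart and during the year do not have this weakness.*

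**Conclusion.** The point holds. Followed as written, the plan schedules no thyroid test during a year of nivolumab at an unchanged 120 mg per week, nor at EOT. The figures of 77–79% by mg and 63–65% of infusions assume 12 or 13 adjuvant doses and a patient who completes the year. The 118-day gap before restart follows directly from footnotes 8 and 9.

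The consequence is a possible delay in detection and a possible undercount of adjuvant-phase thyroid events under objective 1.2.5. It cannot be quantified, because the documents give no thyroid-event rate. The primary endpoint, power and hypothesis test are not affected. The change should be made because the weakness lies in a stated schedule and is cheap to correct, but the point does not threaten the trial's main conclusion.

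**What to change.** Amend the Section 8 calendar to mark thyroid tests:

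1. before the first adjuvant dose;
2. at a regular interval through the adjuvant year, chosen by the investigators and written into the calendar;
3. at EOT.

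State in footnote 17 that TSH and free T4 cover both the neoadjuvant and adjuvant phases. Run them on the blood already drawn for CBC and chemistry, so that no visit is added.

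Illustrative cost for 20 patients, as TSH/free T4 pairs:

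| Schedule | Per patient | Total |
|---|---|---|
| Every third adjuvant dose (about every 12 weeks), plus EOT | 4–5 + 1 = 5–6 | 100–120 |
| Every adjuvant dose, plus EOT | 12–13 + 1 = 13–14 | 260–280 |

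Counting from the first dose, the 12-weekly option already includes the test before restart. The downside is a modest assay cost and more low-grade findings to record and follow.

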# 9 CRITERIA FOR EVALUATION AND ENDPOINT

## 9.1 **Pathological response**

The primary objective of this study will be to identify the pathologic response rate at surgery, including complete response, after 12 weeks of neoadjuvant treatment with nivolumab and HF10. Pathologic response rate will be defined based on the quantity of residual viable tumor in the surgical resection specimen at the time of definitive surgery. A percent viable tumor will be assessed semi-quantitatively in the pre treatment biopsy, on study biopsy at day 42 and the definitive surgical resection specimen by estimating the proportion of residual tumor in relation to the total tumor area and reported as percentage viability (Ribero et al 2007) as per institutional practice. A pathologic complete response will be defined as no viable residual melanoma cells in the surgical specimen. A major pathologic response will be defined as <50% viable tumor cells. A minor pathologic response will be defined as 50% or greater viable tumor cells, including specimens that have 100% viability at surgery. Pathologic response rate (pRR) will be defined as frequency of either pCR or a pathologic major response. This will be compared to the viablity values of the tumor at baseline. Biopsies will be required at Day 0 and at surgery to perform this analysis. A patient must complete the neoadjuvant phase of the trial and complete surgery to be considered evaluable for pathological response.

## 9.2 Safety

Routine safety and tolerability will be evaluated from the results of reported signs and symptoms, scheduled physical examinations, vital sign measurements, and clinical laboratory test results. More frequent safety evaluations may be performed if clinically indicated or at the discretion of the investigator.

## **Physical Examination**

Complete and symptom-directed physical examinations will be performed by a licensed physician (or physician's assistant or nurse practitioner).

## Vital Signs

Vital signs will include (blood pressure, respiratory rate, pulse rate and temperature).

## **Safety Laboratory Determinations**

Laboratory evaluations will be performed as noted in the study calendar.

# 9.3 Recurrence Free Survival

Secondary objectives for this study include recurrence free survival, which is defined as the time from complete surgical resection to the date of the first confirmation of disease reoccurance or death (whichever comes first). Progressive disease will be based on irRC response criteria.

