#### 1.2 Secondary Objectives and Endpoint

1.2.1 Assess recurrence-free survival

Endpoint: recurrence after surgery will be assessed by radiologic scans scheduled per section 8 and confirmed by biopsy.

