# Immune-Related Response Criteria (irRC)

Clinical response assessments will be performed according to irRC (Wolchok, 2009)

Table 1: Overall Response using irRC:

Response Assessment	Description	
irCR	Complete disappearance of all lesions (whether measurable or not, and no new lesions)	
	Confirmation by repeat, consecutive assessment $\geq$ 4 weeks after first documentation.	
irPR	Decrease in tumor burden ≥50% relative to baseline	
	Confirmed by a consecutive assessment $\geq$ 4 weeks after first documentation.	
irSD	Not meeting criteria for irCR or irPR, in absence of irPD. A change in tumor burden of neither 50% decrease from baseline nor 25% increase from nadir can be determined.	
irPD	Increase in tumor burden ≥25% relative to nadir (minimum recorded tumor burden)	
	Confirmation by a repeat, consecutive assessment $\geq 4$ weeks after the first documentation.	

Abbreviations: CR= Complete Response; irRC= Immune-Related Response Criteria; PD= Progressive Disease; PR=Partial Response; SD=Stable Disease

Measurable Response	Non-measurable response		
Target and new, measurable lesions % change in tumor burden	Non-target lesions	New non- measurable lesions	Overall irRC Response
$\downarrow 100^{1}$	Absent	Absent	irCR 
↓ 100 	Stable	Any	irPR 
↓ 100 	Unequivocal progression	Any	irPR 
$\downarrow \ge 50^1$	Absent or Stable	Any	irPR 
$\downarrow \ge 50^1$	Unequivocal progression	Any	irPR 

Table 2: Derivation of irRC overall responses

Protocol name: Phase II Neoadjuvant trial of Nivolumab in Combination with HF10 Oncolytic Viral Therapy in Resectable Stage IIIB, IIIc, IVM1a Melanoma (Neo-NivoHF10) Version Date: 22JUL2019 Principal Investigator: [name]

$\downarrow \ge 50 \text{ to } \uparrow < 25^1$	Absent or Stable	Any	irSD
$\downarrow \ge 50$ to $\uparrow < 25^1$	Unequivocal Progression	Any	irSD
$\uparrow \ge 25^2$	Any	Any	irPD 

Decrease relative to baseline

 Increase relative to nadir

 confirmed by consecutive scan  $\geq$ 4 weeks after first documentation

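### Section 9.3 ties progression for recurrence-free survival to irRC, which conflicts with section 1.2.1 and the calendar and is not usable as written after complete resection

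*Combined protocol and SAP*

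**What the plan says.** Section 9.3 measures RFS as "the time from complete surgical resection to the date of the first confirmation of disease reoccurance or death (whichever comes first"). It then adds "Progressive disease will be based on irRC response criteria".

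Section 1.2.1, the objective for the same endpoint, does not mention irRC: "recurrence after surgery will be assessed by radiologic scans scheduled per section 8 and confirmed by biopsy".

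The irRC tables in section 9.5 define irPD as "Increase in tumor burden ≥25% relative to nadir (minimum recorded tumor burden"), and require "Confirmation by a repeat, consecutive assessment" at least 4 weeks after the increase is first documented. In irRC Table 2 the burden column covers "Target and new, measurable lesions % change in tumor burden". New non-measurable lesions have their own column.

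The study calendar (section 8) marks irRC and RECIST at pre-study and day 84 only. Footnote 19 and section 9.5 place both assessments before surgery, and section 1.3.2 makes the irRC comparison exploratory. Footnote 12 sets scans about every 12 weeks after surgery. Section 10 analyses RFS by Kaplan-Meier, with no hypothesis, event target or decision rule.

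**The concern.** The plan gives two event rules for a named secondary endpoint and no order of precedence. Confirmation in section 9.3 could mean the biopsy of section 1.2.1 or the repeat assessment that irRC requires, and the two give different events and different dates.

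The irRC rule measures change in an existing tumor burden. RFS starts when that burden has been removed. Applied to such patients, it can leave a true recurrence without an event or move its date later. Both effects raise the curve. With 20 planned patients, one event counted or not moves the estimate by about 1/20 = 5 percentage points before censoring.

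**Working it through.** **Plan's own figures.** No figure is stated for RFS, so there is none to reproduce. The only design calculation is for pathologic response in section 10 (20 patients, reject at 4 or more). It reproduces: exact binomial power is 0.589 at a true rate of 20% and 0.893 at 30%, against the stated 59% and 89%. RFS does not enter it.

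**Step 1: irRC with no remaining disease.** Time zero is complete resection. Section 9.8 describes R0 as leaving no gross disease, so measured burden is 0.

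- *Percentage rule.* The change from nadir is (new burden − nadir)/nadir. With nadir 0 the denominator is 0 and the 25% threshold has no value. If nadir were instead taken as the lowest burden recorded before surgery, because irRC is not done afterwards, a recurrence would have to exceed the removed disease by a quarter: for an assumed 60 units, 60 × 1.25 = 75.
- *New non-measurable lesion.* Take burden down 100% from baseline, non-target lesions absent and a new non-measurable lesion. The irCR row fails because it requires no new lesion. The row for a decrease of at least 50%, non-target absent or stable, and any new non-measurable lesion fits, and gives irPR. The irSD row as printed also begins at a 50% decrease and could be read to overlap. Neither result is irPD. That column reads Any in every irPR, irSD and irPD row, so it never decides progression.
- *New measurable lesion.* It does enter the burden. With an assumed baseline of 60 and a new lesion of 15, the change from baseline is (15 − 60)/60 = −75%, which fits irPR. Against a zero nadir the same lesion could be called irPD. The tables do not say which row prevails.
- *Confirmation.* irPD needs a second assessment at least 4 weeks later. If that waits for the next scheduled scan, the gap is about 12 weeks.

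**Step 2: what late dating could do (illustration).** Assume exponential recurrence, no deaths, and a share R recurring by 18 months. Then RFS(t) = (1 − R)^(t/18), and a delay of d months gives RFS(t − d). Four weeks is 4/52 × 12 = 0.92 months; 12 weeks is 2.77 months. R = 60% is the upper figure in section 2.1; R = 40% is assumed.

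| R by 18 months | 12-month RFS, dated at detection | 4 weeks late | 12 weeks late |
|---|---|---|---|
| 60% | 54.3% | 56.9% | 62.5% |
| 40% | 71.1% | 73.0% | 77.0% |

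At R = 60% the median moves from 13.6 to 14.5 or 16.4 months.

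**Step 3: what uncounted recurrences could do (illustration).** If a share m of recurrences is never counted, 18-month RFS is 1 − (1 − m) × 0.60. For m = 10%, 20% and 30% this gives 46%, 52% and 58%, against 40%. The documents support no value of m. The figures are upper limits for a given m, because a small lesion may grow and be counted later, or the patient may die within the window.

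**The case against.** The strongest reply is that the irRC sentence is stray text. The RFS definition speaks of recurrence, not progressive disease; section 1.2.1 says how recurrence is established; and first confirmation can be read as the biopsy. If irRC is never scheduled after surgery, the more direct consequence is ambiguity rather than bias. That is fair as to effect: sites that follow section 1.2.1 may miss few events. It does not remove the conflict, because the sentence stands in the RFS section and nothing tells the analyst to ignore it.

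Several stronger readings are tempting and are not supported.

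- *That reported RFS will be inflated.* This holds only if irRC is actually applied to recurrences.
- *That irRC can never register a recurrence.* New measurable lesions enter the burden, and a reader could call one irPD. New non-measurable lesions do block irCR. The 10 mm limit for measurability comes from section 9.4, which is written for assessments before surgery; the irRC tables give no size limit. Deaths count in any case.
- *That footnote 19 sets a competing RECIST rule for RFS.* Its statement "Only RECIST will be used as clinical response criteria and used to make treatment decisions" follows one about assessments before surgery, and RECIST is not scheduled afterwards either.
- *That optional biopsy at progression contradicts section 1.2.1.* The optional biopsy is the correlative one; a diagnostic biopsy may be separate.

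Precision also limits the practical effect. If 8 of 20 patients were event-free, the exact 95% interval would be roughly 19% to 64%, so a shift from 40% to 46% lies well inside it. The 60% figure is an upper bound for recurrence after resection, whereas patients here also receive neoadjuvant and adjuvant treatment.

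**Conclusion.** The point holds as an inconsistency in the definition of a secondary endpoint. Section 9.3 names a progression rule that conflicts with section 1.2.1, is not scheduled when RFS needs it, and gives an undefined or contradictory result after complete resection.

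The bias is conditional. If section 9.3 is applied literally, some recurrences could be uncounted or dated at least 4 weeks late (about 12 weeks if the next scheduled scan is awaited), and the curve would read too high. How high is unknown. The delay figures assume exponential recurrence and that every event is delayed; the missed shares are hypothetical.

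The pathologic response test, its power and its rule of 4 or more in 20 are unaffected. This should be fixed before RFS is analysed, but it does not threaten the trial's main conclusion.

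**What to change.** 1. Delete the irRC sentence from section 9.3 and keep irRC for the pre-surgical concordance objective.
2. Define the RFS event, in line with section 1.2.1, as the first biopsy-confirmed melanoma recurrence after resection or death. Recurrence means any new local, in-transit, nodal or distant lesion, measurable or not.
3. State one date rule. The date of the scan or examination that first showed the later-confirmed lesion is preferable, because it does not depend on how quickly confirmation follows. Dating at confirmation is a possible choice, but the plan must then say which confirmation is meant.
4. Use the same wording in sections 1.2.1, 9.3 and 10.

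The cost is a short text amendment. Post-surgical scans are already scheduled, so no new visits are needed; the form must hold both the detection date and the confirmation date. RFS may look slightly less favourable than under a literal irRC reading.
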